**Additional Data Obtained at Endpoint Visits**

(In addition to the data collection sheet above for ALL visits, this additional data collection sheet will be used on weeks 6, 12, 24, 32 only)

6 Minute Walk Test	
Distance Walked	_____ (meters)  _____ # of stops (if any)
Stopped Early (before six minutes)	
_____ Yes      _____ No
 
IF "YES" ONLY: (indicating that the patient stopped walking before 6 minutes had elapsed)
 
_____ Time Walked (minutes)
 
_____ Distance Walked (meters)
 
REASON FOR STOPPING EARLY (check only 1 as the "primary reason")
 
_____ Orthopedic/Joint Pain
 
_____ Chest Pain
 
_____ Shortness of Breath
 
_____ Fatigue
 
_____ Leg Pain/Fatigue (not joint related)
 
_____ Dizziness
 
_____ Other

PA pressures immediately after stopping walk	
PA systolic _____ (mmHg)
 
PA diastolic _____ (mmHg)
 
PA mean _____ (mmHg)

PA pressures 5 minutes after stopping exercise	
PA systolic _____ (mmHg)
 
PA diastolic _____ (mmHg)
 
PA mean _____ (mmHg)

PA pressures 10 minutes after stopping exercise	PA systolic _____ (mmHg) PA diastolic _____ (mmHg) PA mean _____ (mmHg)
PA pressures 15 minutes after stopping exercise	PA systolic _____ (mmHg) PA diastolic _____ (mmHg) PA mean _____ (mmHg)
PA pressures 20 minutes after stopping exercise	PA systolic _____ (mmHg) PA diastolic _____ (mmHg) PA mean _____ (mmHg)
PA pressures 25 minutes after stopping exercise	PA systolic _____ (mmHg) PA diastolic _____ (mmHg) PA mean _____ (mmHg)
PA pressures 30 minutes after stopping exercise	PA systolic _____ (mmHg) PA diastolic _____ (mmHg) PA mean _____ (mmHg)
Quality of Life	
KCCQ Score (total)	_____ (points)
Score on Questions 3,7,8,9 which relate to symptoms of congestion	_____ (points)
Double Master's Step test	

Stopped Early (before three minutes)	
_____ Yes      _____ No
 
IF "YES" ONLY: (indicating that the patient stopped climbing before three minutes had elapsed)
 
_____ Time stepping (minutes)
 
_____ Number of trips
 
REASON FOR STOPPING EARLY (check only 1 as the "primary reason")
 
_____ Orthopedic/Joint Pain
 
_____ Chest Pain
 
_____ Shortness of Breath
 
_____ Fatigue
 
_____ Leg Pain/Fatigue (not joint related)
 
_____ Dizziness
 
_____ Other

PA pressures immediately after test	
PA systolic _____ (mmHg)
 
PA diastolic _____ (mmHg)
 
PA mean _____ (mmHg)

PA pressures 5 minutes after stopping test	
PA systolic _____ (mmHg)
 
PA diastolic _____ (mmHg)
 
PA mean _____ (mmHg)

PA pressures 10 minutes after stopping test	
PA systolic _____ (mmHg)
 
PA diastolic _____ (mmHg)
 
PA mean _____ (mmHg)

PA pressures 15 minutes after stopping test	
PA systolic _____ (mmHg)
 
PA diastolic _____ (mmHg)

	PA mean _____ (mmHg)
PA pressures 20 minutes after stopping test	PA systolic _____ (mmHg) PA diastolic _____ (mmHg) PA mean _____ (mmHg)
PA pressures 25 minutes after stopping test	PA systolic _____ (mmHg) PA diastolic _____ (mmHg) PA mean _____ (mmHg)
PA pressures 30 minutes after stopping test	PA systolic _____ (mmHg) PA diastolic _____ (mmHg) PA mean _____ (mmHg)
Handgrip test	
Maximal handrip effort	Max handgrip _____ (Pounds Force)
PA pressures immediately before test	PA systolic _____ (mmHg) PA diastolic _____ (mmHg) PA mean _____ (mmHg)
Blood pressure immediately before test	BP systolic _____ (mmHg) BP diastolic _____ (mmHg)

Heart rate immediately before test	HR _____ (bmp)
PA pressures at 30s of Handrip	PA systolic _____ (mmHg)  PA diastolic _____ (mmHg)  PA mean _____ (mmHg)
Blood pressure at 30s of Handrip	BP systolic _____ (mmHg)  BP diastolic _____ (mmHg)
Heart rate at 30s of Handrip	HR _____ (bmp)
PA pressures at 60s of Handrip	PA systolic _____ (mmHg)  PA diastolic _____ (mmHg)  PA mean _____ (mmHg)
Blood pressure at 60s of Handrip	BP systolic _____ (mmHg)  BP diastolic _____ (mmHg)
Heart rate at 60s of Handrip	HR _____ (bmp)
PA pressures at 90s of Handrip	PA systolic _____ (mmHg)  PA diastolic _____ (mmHg)  PA mean _____ (mmHg)

Blood pressure at 90s of Handrip	BP systolic _____ (mmHg)  BP diastolic _____ (mmHg)
Heart rate at 90s of Handrip	HR _____ (bmp)
PA pressures at 120s of Handrip	PA systolic _____ (mmHg)  PA diastolic _____ (mmHg)  PA mean _____ (mmHg)
Blood pressure at 120s of Handrip	BP systolic _____ (mmHg)  BP diastolic _____ (mmHg)
Heart rate at 120s of Handrip	HR _____ (bmp)
PA pressures 5 minutes after stopping the test	PA systolic _____ (mmHg)  PA diastolic _____ (mmHg)  PA mean _____ (mmHg)
Blood pressure 5 minutes after stopping the test	BP systolic _____ (mmHg)  BP diastolic _____ (mmHg)
Heart rate 5 minutes after stopping the test	HR _____ (bmp)
PA pressures 10 minutes after stopping the test	PA systolic _____ (mmHg)

	PA diastolic _____ (mmHg)  PA mean _____ (mmHg)
Blood pressure 10 minutes after stopping the test	BP systolic _____ (mmHg)  BP diastolic _____ (mmHg)
Heart rate 10 minutes after stopping the test	HR _____ (bpm)
PA pressures 15 minutes after stopping the test	PA systolic _____ (mmHg)  PA diastolic _____ (mmHg)  PA mean _____ (mmHg)
Blood pressure 15 minutes after stopping the test	BP systolic _____ (mmHg)  BP diastolic _____ (mmHg)
Heart rate 15 minutes after stopping the test	HR _____ (bpm)
Stroop Color test	
PA pressures immediately before test	PA systolic _____ (mmHg)  PA diastolic _____ (mmHg)  PA mean _____ (mmHg)

Blood pressure immediately before test	BP systolic _____ (mmHg)  BP diastolic _____ (mmHg)
Heart rate immediately before test	HR _____(bmp)
PA pressures at 30s of Stroop Color test	PA systolic _____ (mmHg)  PA diastolic _____ (mmHg)  PA mean _____ (mmHg)
Blood pressure at 30s of Stroop Color test	BP systolic _____ (mmHg)  BP diastolic _____ (mmHg)
Heart rate at 30s of Stroop Color test	HR _____(bmp)
PA pressures at 60s of Stroop Color test	PA systolic _____ (mmHg)  PA diastolic _____ (mmHg)  PA mean _____ (mmHg)
Blood pressure at 60s of Stroop Color test	BP systolic _____ (mmHg)  BP diastolic _____ (mmHg)
Heart rate at 60s of Stroop Color test	HR _____(bmp)

PA pressures at 90s of Stroop Color test	PA systolic _____ (mmHg)  PA diastolic _____ (mmHg)  PA mean _____ (mmHg)
Blood pressure at 90s of Stroop Color test	BP systolic _____ (mmHg)  BP diastolic _____ (mmHg)
Heart rate at 90s of Stroop Color test	HR _____ (bmp)
PA pressures at 120s of Stroop Color test	PA systolic _____ (mmHg)  PA diastolic _____ (mmHg)  PA mean _____ (mmHg)
Blood pressure at 120s of Stroop Color test	BP systolic _____ (mmHg)  BP diastolic _____ (mmHg)
Heart rate at 120s of Stroop Color test	HR _____ (bmp)
PA pressures at 150s of Stroop Color test	PA systolic _____ (mmHg)  PA diastolic _____ (mmHg)  PA mean _____ (mmHg)

Blood pressure at 150s of Stroop Color test	BP systolic _____ (mmHg)  BP diastolic _____ (mmHg)
Heart rate at 150s of Stroop Color test	HR _____ (bpm)
PA pressures at 180s of Stroop Color test	PA systolic _____ (mmHg)  PA diastolic _____ (mmHg)  PA mean _____ (mmHg)
Blood pressure at 180s of Stroop Color test	BP systolic _____ (mmHg)  BP diastolic _____ (mmHg)
Heart rate at 180s of Stroop Color test	HR _____ (bpm)
Level of difficulty	( ) non-stressful ( ) slightly stressful ( ) moderately stressful ( ) very stressful ( ) extremely stressful.
PA pressures 5 minutes after stopping the test	PA systolic _____ (mmHg)  PA diastolic _____ (mmHg)  PA mean _____ (mmHg)
Blood pressure 5 minutes after stopping the test	BP systolic _____ (mmHg)  BP diastolic _____ (mmHg)

Heart rate 5 minutes after stopping the test	HR _____(bmp)
PA pressures 10 minutes after stopping the test	PA systolic _____ (mmHg)  PA diastolic _____ (mmHg)  PA mean _____ (mmHg)
Blood pressure 10 minutes after stopping the test	BP systolic _____ (mmHg)  BP diastolic _____ (mmHg)
Heart rate 10 minutes after stopping the test	HR _____(bmp)
PA pressures 15 minutes after stopping the test	PA systolic _____ (mmHg)  PA diastolic _____ (mmHg)  PA mean _____ (mmHg)
Blood pressure 15 minutes after stopping the test	BP systolic _____ (mmHg)  BP diastolic _____ (mmHg)
Heart rate 15 minutes after stopping the test	HR _____(bmp)
Laboratory Data (natriuretic peptides)	
NT-proBNP	_____ (ng/L)

*Additional Lab Data*

*(Collected on Weeks 2, 6, 8, 12, 24, 32 or after ANY adjustment of study medication or if otherwise indicated for standard care)*

Laboratory Data	
Serum Sodium	_____ (in clinic, mEq/L)
Serum Potassium	_____ (in clinic, mEq/L)
Blood Urea Nitrogen	_____ (in clinic, mEq/L)
Serum Creatinine	_____ (in clinic, mEq/L)

## Study Endpoints

### *Co-Primary Endpoints:*

#### Intensive Phase:

- Difference between mean change in PAPm after 6 weeks on Entresto compared to 6 weeks on continued ACEI/ARB

#### Acute First-Day Response

- Change in PAPm between baseline and first 3 hours after the first dose of Entresto

### *Secondary Endpoints:*

- The mean change in PAPm in both groups on Entresto from week 12 to week 32 in longitudinal study
- Difference between mean change in PAPm from baseline on ACEI/ARB to 6 weeks on Entresto (groups A and B)
- \*Change in exercise recovery PAPm
- \*Change PAPm, blood pressure and heart rate during isometric exercise and recovery after isometric exercise.
- Change PAPm, blood pressure and heart rate during isometric exercise and recovery after mental stress challenge.
- \*Change in NT-proBNP and the BNP/NT-proBNP ratio

#### Tertiary Endpoints (Exploratory):

- Relationship of change in PAPm to change in the questions in the Kansas City Cardiomyopathy Questionnaire (KCCQ) 3, 7,8,9 which describe the severity of symptoms of congestion
- Mean change in total daily diuretic dose while on Entresto

### *Other Endpoints:*

- *Death*
- *All-cause re-hospitalization*
- *Need to progress to advanced therapies (i.e. start home inotropes, place a ventricular assist device or list for cardiac transplantation)*
- *Unscheduled visits for IV loop diuretics*
- *Other interventions (i.e. nutrition referrals)*

*\*Will be 3 comparisons:*

- 1) 6 weeks of Entresto vs 6 weeks of continued ACEI/ARB (Group A compared to B at 6 weeks)
- 2) Baseline on ACEI/ARB compared to 6 weeks on Entresto (Groups A and B combined)
- 3) 12 weeks on Entresto compared to 32 weeks on Entresto in longitudinal study (all pts)

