#### *Secondary Objectives:*

- Determine the mean change in PAPm in both groups on Entresto from week 12 to week 32 in longitudinal study
- Determine the difference between mean change in PAPm from baseline on ACEI/ARB to 6 weeks on Entresto (Groups A and B)
- \*Determine the change in distance walked during and the change in exercise recovery PAPm after a standard 6 minute walk test
- \*Determine the impact of therapy over time on double Master's Step test, assessing changes in PAPm during recovery after test.
- \*Determine the impact of therapy over time on Handgrip Test, assessing changes in PAPm, blood pressure and heart rate during isometric exercise and recovery after test.
- \*Determine the impact of therapy over time on Stroop Color Test, assessing changes in PAPm, blood pressure and heart rate during mental stress challenge and recovery after test.
- \*Determine the change in NT-proBNP and the BNP/NT-proBNP ratio

*Tertiary Objectives (Exploratory):*

- Examine the relationship of change in PAPm to change in the questions in the Kansas City Cardiomyopathy Questionnaire (KCCQ) 3, 7,8,9 which describe the severity of symptoms of congestion
- Determine the mean change in total daily diuretic dose while on Entresto

*\*Will be 3 comparisons:*

- 1) 6 weeks of Entresto vs 6 weeks of continued ACEI/ARB (Group A compared to B at 6 weeks)
- 2) Baseline on ACEI/ARB compared to 6 weeks on Entresto (Groups A and B combined)
- 3) 12 weeks on Entresto compared to 32 weeks on Entresto in longitudinal study (all pts)\

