  - Statistical Plan (*Intensive Phase, patients in both groups as their own control after 6 weeks of Entresto- Group A: week 6 minus baseline; Group B: week 12 minus week 6*): The change in PAPm from pre to peak exercise at baseline and at 5 minute intervals for 30 minutes of recovery will be compared to the change in PAPm from pre to peak exercise and at 5 minute intervals for 30 minutes of recovery at 6 weeks in Group A. If the distributions are normal, the results will be presented as means with standard errors. If the distributions are not normal, the results will be presented as medians with interquartile ranges. The change in PAPm from pre to peak exercise at 6 weeks and at 5 minute intervals for 30 minutes of recovery will be compared to the change in PAPm from pre to peak exercise and at 5 minute intervals for 30 minutes of recovery at week 12 in Group B. If the distributions are normal, the results will be presented as means with standard errors. If the distributions are not normal, the results will be presented as medians with interquartile ranges.

- Statistical Plan (*Intensive Phase, patients on the Entresto Group A: week 6 minus baseline*) compared to patients on continued ACEi/ARB therapy; Group B: week 6 minus baseline): The change in PAPm from pre to peak exercise and at 5 minute intervals for 30 minutes of recovery at 6 weeks in Group A will be compared to the change in PAPm from pre to peak exercise and at 5 minute intervals for 30 minutes of recovery at 6 weeks in Group B. If both distributions are normal, t-testing will be performed to compare the mean changes between groups. If the distributions are not normal, Wilcoxon testing will be used.  $P < 0.05$  will be significant.
- Statistical Plan (*Longitudinal Phase, Patients in both groups - week 32 minus week 12*): The change in PAPm from pre to peak exercise and at 5 minute intervals for 30 minutes of recovery at 32 weeks will be compared to the change in PAPm from pre to peak exercise and at 5 minute intervals for 30 minutes of recovery at 12 weeks in both groups. If the distributions are normal, the results will be presented as means with standard errors. If the distributions are not normal, the results will be presented as medians with interquartile ranges.
- *Determine the impact of therapy over time on standard double Master's step test, assessing changes in PAPm during recovery after the test.*

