  - *Statistical Plan (Intensive Phase, patients on the Entresto Group A: week 6 minus baseline) compared to patients on continued ACEi/ARB therapy; Group B: week 6 minus baseline):* The change in PAPm, blood pressure and heart rate during Stroop Color test and at 5 minute intervals for 15 minutes of recovery at 6 weeks in Group A will be compared to the change in PAPm, blood pressure and heart rate during Stroop Color test and at 5 minute intervals for 15 minutes of recovery at 6 weeks in Group B. If both distributions are normal, t-testing will be performed to compare the mean changes between groups. If the distributions are not normal, Wilcoxon testing will be used.  $P < 0.05$  will be significant.
  - *Statistical Plan (Longitudinal Phase, Patients in both groups - week 32 minus week 12):* The change in PAPm, blood pressure and heart rate during Stroop Color test and at 5 minute intervals for 15 minutes of recovery at 32 weeks will be compared to the change in PAPm, blood pressure and heart rate during Stroop Color test and at 5 minute intervals for 15 minutes of recovery at 12 weeks in both groups. If the distributions are normal, the results will be presented as means with

standard errors. If the distributions are not normal, the results will be presented as medians with interquartile ranges.

- *Determine the change in NT-proBNP and the BNP/NT-proBNP ratio*
  - Statistical Plan (*Intensive Phase, patients in both groups as their own control - Group A: week 4 minus baseline; Group B: week 8 minus week 4*) The change in NT-proBNP from baseline to week 6 will be assessed in Group A and combined with the change in NT-proBNP levels from week 6 to week 12 in Group B. These distributions will be continuous distributions. If the distributions are normal, the results will be presented as means with standard errors. If the distributions are not normal, the results will be presented as medians with interquartile ranges.
  - Statistical (*Intensive Phase, patients on the Entresto Group A: week 6 minus baseline) compared to patients on continued ACEi/ARB therapy; Group B: week 6 minus baseline*): The change in NT-proBNP levels will be assessed from baseline to week 6 in Group A and Group B. If both distributions are normal, t-testing will be performed to compare the mean changes between groups. If the distributions are not normal, Wilcoxon testing will be used.  $P < 0.05$  will be significant.

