## Power Analysis

There will be 20 patients total, 10 in each group.

*Between group comparison:* This sample size will provide 90% power with 2-sided alpha of 0.05 to detect a 20% difference between the 2 groups (Entresto and ACEI/ARB) in the PAPm change at 6 weeks, based on an assumed baseline PAPm of 25 mm, using a t-test with a standard deviation in the mean change of as high as 3.4. We do not yet have data on which to estimate the standard deviation of this change, but we have found a standard deviation of 3-4 mm Hg of PAPm pressures during 5 day periods in stable patients followed on Cardiomems devices at Brigham and Women's Hospital (unpublished data).

*All patients after 6 weeks of Entresto compared to chronic ACEI/ARB at baseline:* There is additional power for this highest secondary endpoint. Assuming the PAPm baseline on ACEI/ARB mean of 25mm, a sample size of 20 patients will provide 90% power with two-sided alpha of 0.05 paired t-test to detect a 20% decrease (to PAPm of 20 mm) after 6 weeks of Entresto, with a standard deviation for the change as high as 6.8.

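### Comparison 2 for the walk, step, handgrip and Stroop tests is defined with Groups A and B combined, but the analysis text summarises each group of 10 separately

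*Combined protocol and SAP*

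**What the plan says.** In section II.a of the protocol, Secondary Objectives, an asterisk marks the six-minute walk, double Master's step, handgrip and Stroop objectives as well as NT-proBNP. The Stroop item, for example, opens "Determine the impact of therapy over time on Stroop Color Test". The asterisk leads to three comparisons, of which the second is "Baseline on ACEI/ARB compared to 6 weeks on Entresto (Groups A and B combined"). The same definition is repeated after Other Endpoints in the Study Endpoints section. The endpoint list there is less tidy: the mental-stress (Stroop) bullet has no asterisk, and the step test is not named. The promise for all four tests therefore rests mainly on II.a.

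Under Statistical Analysis, Secondary Endpoints, each of the four tests has an entry in which patients serve as their own controls. The difference is week 6 minus baseline in Group A and week 12 minus week 6 in Group B. In every one of these entries Group A is described and given its own reporting rule ("recovery at 6 weeks in Group A. If the distributions are normal, the results will be presented as means with standard errors", otherwise medians with interquartile ranges). Group B is then described and given the same rule a second time.

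The NT-proBNP entry differs. Group A's change is "combined with the change in NT-proBNP levels from week 6 to week 12 in Group B". The entry for resting mean pulmonary artery pressure (PAPm) pools the groups in the same way. On size, the Power Analysis states "There will be 20 patients total, 10 in each group".

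**The concern.** The definition of the comparison and the instructions for computing it disagree. An analyst working from the four entries alone would produce two sets of results per test and no combined one. The choice between mean and median is also made separately in each group, so Group A could be reported as a mean and Group B as a median for the same quantity.

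At stake is the precision of four secondary endpoints in a small trial. With 10 patients, the two groups can differ noticeably by chance. Each test also has several readings: for the walk, the pre-to-peak change plus six recovery readings, so 7 combined figures become 14 group-specific ones.

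**Working it through.** **1. The entries side by side**

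| Endpoint | Asterisk in II.a | Own-control entry in Statistical Analysis |
|---|---|---|
| Six-minute walk, PAPm | yes | A and B summarised separately |
| Six-minute walk, distance | yes | none |
| Double Master's step | yes | A and B summarised separately |
| Handgrip | yes | A and B summarised separately |
| Stroop | yes | A and B summarised separately |
| NT-proBNP | yes | A and B combined |
| Resting PAPm | no (own objective covering both groups) | A and B combined |

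Of the asterisked objectives, only NT-proBNP receives the combined analysis that comparison 2 calls for.

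**2. The plan's own figure for a combined own-control comparison**

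The Power Analysis says of resting PAPm that "a sample size of 20 patients will provide 90% power with two-sided alpha of 0.05 paired t-test to detect a 20% decrease", "with a standard deviation for the change as high as 6.8". Inputs: n = 20, change 25 − 20 = 5 mm Hg, SD 6.8, two-sided alpha 0.05.

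- Normal approximation: Φ(5/6.8 × √20 − 1.96) = Φ(1.33) = 90.8%, which reproduces the stated 90%.
- Exact noncentral t with 19 degrees of freedom: 87.7%.

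This figure belongs to resting PAPm, which the analysis text does pool. It is shown to confirm that the plan sizes its own-control comparison on all 20 patients.

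**3. Precision, 10 against 20 patients**

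The 95% half-width for a mean paired difference is t(0.975, n−1) × SD/√n.

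- n = 10: t(0.975, 9)/√10 = 0.715 SD
- n = 20: t(0.975, 19)/√20 = 0.468 SD
- Ratio 0.715/0.468 = 1.53; reduction 1 − 0.468/0.715 = 35%
- Standard error ratio: √20/√10 = 1.41

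These ratios do not depend on the SD.

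**4. On the mm Hg scale, by assumption**

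The documents give no SD for the response to any of the four tests. As a stand-in for the PAPm quantities only, I take 3 to 6.8 mm Hg from the resting-PAPm figures in the Power Analysis. That range includes the between-group input, "using a t-test with a standard deviation in the mean change of as high as 3.4".

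| Assumed SD | Half-width, n = 10 | Half-width, n = 20 |
|---|---|---|
| 3 | 2.15 | 1.40 |
| 3.4 | 2.43 | 1.59 |
| 6.8 | 4.86 | 3.18 |

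Estimating the variance within groups (18 degrees of freedom) changes the last figure only from 3.18 to 3.19, so the pooling method hardly matters.

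**The case against.** The strongest reply is that only a sentence is missing. The objectives and endpoints sections state the target, the four entries are introduced as covering both groups, and each group's subtraction is given. A reader might infer that the combined comparison can never be obtained, or that nothing says which result answers it. The documents do not support that, because II.a and Study Endpoints name the combined comparison. When both groups are reported as means, it can also be rebuilt: with 10 per group the combined mean is the average of the two, with standard error √(SE_A² + SE_B²)/2. It cannot be rebuilt from medians, or from one mean and one median, without returning to patient data.

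A reader might also infer a loss of power. Borrowing the resting-PAPm inputs, an exact paired t-test would have 54.6% power with 10 patients and 87.7% with 20. But the own-control entries for these tests prescribe no test and no threshold; P < 0.05 appears only in the between-group entries. Those percentages are therefore not properties of this plan, and no stated power figure changes.

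Finally, separate display has a rationale. Group B's reference is week 6, after further titrated ACEi/ARB plus placebo and a second round of testing, whereas Group A's is the enrolment baseline. That supports showing both groups. It is not a reason to omit the combined figure, since the plan already pools across these two references for resting PAPm and NT-proBNP.

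**Conclusion.** The inconsistency stands for all four tests, on the strength of the asterisks in II.a. The analysis text does not deliver comparison 2 as defined. Taken literally, it replaces an estimate over 20 patients with summaries of 10, whose 95% intervals have a half-width of 0.72 SD instead of 0.47 SD. This assumes equal SDs in the two groups, a similar mean change in each, and no dropout. Walk distance is a further gap, since it is asterisked but has no own-control analysis.

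The matter is confined to descriptive, uncontrolled secondary summaries in a pilot. No primary result, significance claim or data collection is touched. It is still worth correcting before analysis, because it costs little and settles what is to be reported.

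**What to change.** In the own-control entries for the walk, step, handgrip and Stroop tests:

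- For each quantity already specified (pre-to-peak or during-test change, and each recovery time point; for handgrip and Stroop also blood pressure and heart rate), compute each patient's paired difference: week 6 minus baseline in Group A, week 12 minus week 6 in Group B.
- Report the combined estimate over all 20 patients as comparison 2. Give the mean with standard error and 95% confidence interval, or the median with interquartile range if the combined distribution is not normal, applying the normality check to the combined distribution as the resting-PAPm entry does.
- Add the same analysis for walk distance.
- Label the result an uncontrolled pre/post change in which Group B's reference is week 6, not study baseline.
- Keep the by-group results as supporting displays.

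It would also help to make the Study Endpoints list agree with II.a by marking the Stroop bullet and naming the step test.

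The cost is wording only, with no new data or visits. The small downside is that the combined figure is uncontrolled and mixes two reference points, as the plan's other pooled endpoints already do.
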